- (1) not received potentially curative treatment; or
- (2) there is evidence that the treatment has not been curative (e.g. recurrent or progressive disease); or
 - A treated cancer is cured should be made by an experienced clinician, with the decision requiring a disease-free interval of follow-up.
- (3) treatment is ongoing.

Standardized 2-week in-patient rehabilitation

- Breathing exercises,
- Bronchial hygiene,
- Health education,
- Bike exercise for 20 minutes (excluding history of hip operation done)
- Walking exercise at least 50m or as tolerated
- Activity of daily living training by Occupational Therapists
- Dietitian referral if needed, to ensure adequate nutrient intake.

A standardized resistance training (Patterson, 2019)

- Exercise: Isotonic knee extension
- Sessions per week: 6 (Except Sunday and public holiday)
- Duration of intervention: 2 weeks
- Total number of sessions during hospitalization: 12 sessions
- Sets per session: 4 (Total Repetitions: 75reps in total across 4 sets)
- Rest between sets: 30s
- Execution speed: 1-2s
- Load: 15-30% of 1 repetition maximum(1-RM) (Loenneke, 2012)

- Involvement of limb per session: Alternate limb training on alternate day
- Execution: until planned rep scheme is completed or contraction failure
- Remarks: If at any time the patient becomes dizzy, severe discomfort (e.g. pain, numbness), training will be stopped.

The BFR-RE intervention group (Patterson, 2019)

The participants will have the above-mentioned resistance training with “BFR-device” with details as follows:

- Cuff size: medium
- Restriction time: 5- 10 mins (stop after finishing 4 sets of training or terminating by Physiotherapists)
- Applied location: alternate quadriceps in consecutive day
- Applied pressure: 80% limb occlusion pressure (LOP)

Control group

Same standardized 2-week in-patient rehabilitation and same amount of the above-mentioned resistance training without the “BFR device”.

Determination of maximal voluntary isometric contraction (MVIC) (Hul, 2004)

- Maximal voluntary isometric contraction (MVIC) is the simplest way to measure the force-producing capabilities of a muscle group objectively during its isometric contraction condition which means muscle group under contraction with a constant velocity of joint motion and muscle length. (The National Isometric Muscle Strength (NIMS) Database Consortium, 1996)

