- The 3rd generation tourniquet system features a built-in LOP measurement capability. This allows a personalized tourniquet pressure for each individual patient and eliminated the need to account for cuff width, limb size or blood pressure.

Determination of Leg dominance (Melick, 2017)

Since mobility is a bilateral mobilizing task, the leg dominance will be defined by the participant's preferred leg to shoot a ball when being asked the following question: "If you would shoot a ball on a target, which leg would you use to shoot the ball?"

Determination of completeness of training

80% of the whole course of in-patient additional muscle strength training (i.e. 10 out of 12 sessions)

Determination of acceptance of program

5-point Likert scale will be given to participants after the additional muscle strength training (i.e. very like, like, no comment, dislike, very dislike)

Data collection timepoint

- Baseline
- After completeness of training (i.e. at least 10 sessions of training)

Clinical investigations

- Laboratory tests at baseline and post training program
 - ✧ Clotting profile, Complete blood count (CBC), liver function test (LFT), renal function test (RFT), serum creatinine kinase level (CK), serum lactic acid level, C-reactive protein (CRP)
 - ✧ Estimated 32ml of venous blood in total will be needed for both pre and post training blood tests.
 - ✧ Myoglobin in urine
- Spirometry before discharge of current admission

Primary outcome:

Localized Muscle Strength (Robles, 2011; Hul ,2004)

- Muscle strength is operationally defined as subject's capability for the exertion of force or torque to an external dynamometer over a specified period of time. (Kroemer, 1980)
- Maximal voluntary isometric contraction (MVIC) of knee extension of the dominant leg, with a unit Newton (N), will be assessed by computer dynamometry.

Secondary outcomes:

- **Functional test**
 - ✧ Short physical performance battery (SPPB) (Mora, 2015)
Gait speed with 4m distance, Balance test & repeated chair stands test
 - ✧ 6-minute walk test (Holland, 2010)
- **Systemic muscle strength** (Jeong, 2017; Yu, 2017)
 - ✧ Hand grip strength, a non-invasive marker of systemic skeletal muscle strength and function, is assessed by handheld grip dynamometer of dominant hand
- **Health related quality of life**
 - ✧ Self-administered Chinese version of COPD assessment test (CAT) (Karlah,2016)
- **Acceptability of BFR-RE**

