 - ✧ Pain by visual analog scale (0-10) before, immediate and 5-min post exercise
 - ✧ Participant's acceptance by a Likert 5-point categorical scale after the whole program
- **Feasibility of BFR-RE**
 - ✧ Examination of drop-out rate and reasons of drop-out in those discontinuing the training
- **Unplanned readmission rate within 1 month of discharge for COPDAE**

Data analysis

SPSS version 17.0 will be used for statistical analysis.

The comparison of baseline characteristics of subjects across the 2 groups will be tested by independent t-test for continuous variables (e.g. age, anthropologic data, maximum voluntary isometric contraction of knee extension of dominant leg, hand grip strength of dominant hand, laboratory test results, spirometry data, 6-minute walk test, COPD Assessment test (CAT), etc.), Chi-square test for nominal variables (e.g. presence of myoglobin in urine, etc.).

For testing between-group and within-group changes after Blood flow restriction resistance exercise (BFR-RE), multivariate repeated measures ANOVA will be used.

All continuous variables are presented as mean \pm SD (standard deviation). The level of statistical significance was set at $p < 0.05$.

Sample size calculation

A priori power analysis (calculated by G*Power 3.1.9.5) showed that in order to have a power of 80% to detect a difference of medium effect (f^2 : 0.22) of muscle strength gain (Cook, 2017) at the 0.05 level of significance, 18 patients is needed in each group. If a dropout rate of 30% is estimated, 48 patients in total will be needed for the study.

Randomization

Participants are randomized into one of the two treatment groups. A computer compiles randomization list. Based on randomization, envelopes are made with participant number, including allocation of patients to BFR-RE vs. without BFR-RE. The envelopes are opened after inclusion for the individual participant only. The randomization list is kept in a sealed envelope.

Stratification of participants into two groups by maximum voluntary isometric contraction (MVIC) at baseline before randomization will be done. The cutoff for the stratification will be determined from the data in the recent service.

Blinding

Participants, doctors, nurses and involved Physiotherapists are for obvious reasons not blinded, but assessments at recruitment and on discharge will be carried out by blinded Physiotherapists without knowledge of treatment group.

Interruption

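### For a participant who stops before 10 sessions, the plan does not settle whether post-training MVIC is measured, and no analysis set or missing-data rule says how that participant enters the primary comparison

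*Combined protocol and SAP*

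**What the plan says.** All references are to the combined protocol and SAP.

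- **Data collection timepoint** lists two points: baseline, and "After completeness of training (i.e. at least 10 sessions of training".
- **Determination of completeness of training** defines completeness as "80% of the whole course of in-patient additional muscle strength training (i.e. 10 out of 12 sessions". The resistance training section gives the denominator: "Total number of sessions during hospitalization: 12 sessions".
- **Blinding** says that "assessments at recruitment and on discharge will be carried out by blinded Physiotherapists without knowledge of treatment group". It names no outcomes and sets no minimum number of sessions. The same section says that "Participants, doctors, nurses and involved Physiotherapists are for obvious reasons not blinded".
- **Data analysis** says that for changes between and within groups "multivariate repeated measures ANOVA will be used". Apart from that it gives baseline tests, the software, the presentation of continuous data and the significance level. It defines no analysis set and no rule for missing values.
- **Sample size calculation** requires 18 per group and adds: "If a dropout rate of 30% is estimated, 48 patients in total will be needed for the study".
- **Secondary outcomes** already include the drop-out rate and its reasons, as a measure of feasibility.
- **Interruption** allows withdrawal by the participant and exclusion by the investigator at any time.

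**The concern.** Take a participant who stops after six sessions and stays on the ward. Under the data collection section no post-training MVIC is due. Under the Blinding section one is. The same holds for SPPB, 6-minute walk and grip strength. CAT is self-administered, so its discharge timing can only be inferred.

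A repeated measures ANOVA on two times needs both values. If early stoppers are not measured, they leave the primary analysis, and a comparison set up by randomisation becomes one between people who tolerated at least 10 sessions. Whether someone reaches 10 sessions is decided after randomisation and may depend on the arm.

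Two things follow. The estimate may be biased if loss differs by arm, and a measurement that was never taken cannot be recovered at analysis. Also, with no analysis set written down, who counts in the primary result can be decided after the data are seen.

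**Working it through.** **1. The two rules side by side**

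| Participant | Data collection section | Blinding section |
|---|---|---|
| At least 10 sessions, then discharged | measured | measured at discharge |
| At least 10 sessions, stays on, then discharged | measured; no upper time limit is given | measured at discharge |
| Fewer than 10 sessions, still on the ward | no post-training point | measured at discharge |
| Withdrawn, excluded, transferred or died | no post-training point if before 10 sessions | may also be unmeasured |

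Only the third row is a conflict.

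**2. The plan's own numbers.** Reading f² = 0.22 as an effect for two equal groups, d = 2 × √0.22 = 0.938. The usual normal-approximation formula (two-sided 5%, 80% power) gives 18 per group, as stated. The exact t-test has 78% power at 18 and needs 19. The total of 48 follows from 18 × 1.3 = 23.4, rounded up to 24 per group. At 30% loss, 24 × 0.30 = 7.2, so about 7 per arm lack a second value and about 17 remain.

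**3. Bias if only completers are analysed.** The documents give no drop-out by arm, so every input here is assumed. Let there be no true effect. Let each participant have a latent normal tendency to stay that correlates r with the gain in MVIC. With loss p, completers in that arm have a mean gain above the arm's true mean by r × φ(z_p)/(1 − p), in SD of gain. The bias is the difference between arms.

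- φ(z_p)/(1 − p): 0.644 at p = 0.40; 0.570 at 0.35; 0.424 at 0.25; 0.350 at 0.20.
- 40% versus 20%: r × (0.644 − 0.350) = 0.088, 0.147, 0.206 for r = 0.3, 0.5, 0.7.
- 35% versus 25%: r × (0.570 − 0.424) = 0.044, 0.073, 0.102.
- 30% versus 30%: 0.

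The bias favours the arm with more loss, so it can go either way.

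What r means: stoppers gain less than completers by r × φ(z_p)/[p(1 − p)]. At r = 0.3 this is about 0.5 SD. At r = 0.7 it is 0.7 × 0.386/0.24 = 1.13 SD at 40% loss and 0.7 × 0.280/0.16 = 1.22 SD at 20% loss. That exceeds the whole planned effect of 0.94, so the upper end is severe.

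**4. Type I error** (simulation, 40,000 replicates, 24 per arm, t-test on gain, which equals the group-by-time test with two times; r = 0.3, 0.5, 0.7):

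- 40% versus 20%: 5.7%, 7.2%, 10.0%.
- 35% versus 25%: 5.5%, 5.5%, 6.4%.
- 30% versus 30%: 4.9%, 4.9%, 5.0%.

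**5. Effect of measuring stoppers.** If a random share q of them is assessed, the bias term for each arm becomes r × φ(z_p)(1 − q)/[(1 − p) + pq]. At 40% versus 20% and q = 0.5 the bias falls to 0.026, 0.043, 0.060 SD, with type I error of 5.1% to 5.4%.

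**6. Power at d = 0.938**

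| Analysed | Assumption | Power |
|---|---|---|
| 17 per arm | completers only | 0.76 |
| 24 per arm | no dilution | 0.89 |
| 24 per arm | 15% dilution, d = 0.797 | 0.77 |
| 24 per arm | the 30% who stop gain nothing, d = 0.657, SD unchanged | 0.61 |
| 24 per arm | same, with the larger SD of a mixed BFR arm (simulated) | 0.57 |

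**The case against.** The strongest reply is that the Blinding section already provides a discharge assessment for everyone. Exclusion 14 removes patients expected to stay under 2 weeks, so many early stoppers should still be on the ward to receive it. Drop-out and its reasons are already an outcome. On that view the 10-session wording is loose drafting. This is a fair reading and may be what the sponsor intends, but the documents do not say so. Even if it is right, the analysis set and the handling of missing values remain unstated.

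Several stronger readings are tempting and are not supported:

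- *The sections also conflict for participants who finish training and stay on.* They do not. The data collection point has no upper limit, so a discharge assessment satisfies both.
- *Seven of 24 per arm are lost because of the wording.* That treats the whole 30% as early stoppers who could have been measured. Those who withdraw, are excluded, are transferred or die may be missing under either section. Seven is an upper guide under the plan's own drop-out assumption.
- *Training is stopped for good when symptoms occur.* The remark on dizziness and severe discomfort follows per-session instructions and may refer to that session only.
- *The primary result will be biased.* No drop-out by arm is given. Differential loss is plausible: the arms are unblinded, and the safety section ties numbness (up to 18.5%) to tourniquet pressure and cites 14.6% fainting or dizziness with BFR-RE. Plausible is not demonstrated.

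**Conclusion.** The point stands for early stoppers and should be fixed. For them the two sections give different answers on whether the primary outcome is measured, and nothing else in the document resolves it. The lack of an analysis set and of a missing-data rule is certain from the text.

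The bias is a risk of unknown direction and size, and is nil if loss is equal and arises by the same mechanism in both arms. Under the assumed scenarios it is modest at 35% versus 25% loss (0.04 to 0.10 SD, type I error 5% to 6%). It is larger at 40% versus 20% (0.09 to 0.21 SD, about 6% to 10%), with the top of that range needing stoppers to gain 1.1 to 1.2 SD less than completers. The power figures rest on one reading of f² = 0.22 and on a two-sided test, which the plan does not state.

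**What to change.** 1. Reconcile the two sections: apply the blinded discharge assessment to all randomised participants, whatever the number of sessions completed. Record days from randomisation to assessment by arm, because discharge is decided by unblinded staff. A fixed day after randomisation is an alternative. It would have to fit 12 sessions at "Sessions per week: 6 (Except Sunday and public holiday", which take 13 to 14 calendar days from the first session when no public holiday intervenes.
2. State that stopping training does not end outcome assessment unless consent is withdrawn.
3. Make the primary analysis all randomised participants in their allocated arm. Keep the set with at least 10 sessions as a secondary per-protocol analysis.
4. For MVIC that is still missing, name the primary method and its assumption. Add a sensitivity analysis that shifts the missing gains separately by arm. With 17 of 24 measured, a 1 SD shift in one arm moves the estimate by 7/24 = 0.29 SD, and opposite shifts in both arms by 14/24 = 0.58 SD.
5. Report the already planned drop-out rate and reasons by arm, with the number of early stoppers assessed.

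The cost is protocol wording and some extra assessments by blinded physiotherapists already in place. Not every stopper will be reachable. Counting partly treated participants may dilute the effect: with all 24 per arm assessed, power runs from 0.89 with no dilution to 0.57 to 0.61 if the 30% who stop gain nothing. Restate the power for the analysis set chosen.

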- Computer dynamometer will be used to measure the MVIC of the isometric knee extension of the dominant leg.
- Patient will be seated in hip flexion of 90°, knee flexion of 90°, and the padded force transducer set around malleolus. The lever arm (distance between the force transducer and the point of rotation) will be recorded for calculation of force produced by the computer dynamometer.
- Upper body will be stabilized and verbal encouragement will be given to the participants in a standardized way.
- 3 submaximal warm-up contractions trials will be given with 1-minute rest afterwards.

- 3 trials of MVIC with 1 min of rest between each trial will be instructed. After a build-up phase of 2 s, an MVIC needs to be in a steady, maximal contraction, with a plateau phase of 3 s.
- During measurements, the Physiotherapists can have visual feedback of the force signal, monitoring the quality of the shape of each contraction.
- The highest value for MVIC will be captured for future analysis.

Determination of 1-repetition maximum (1-RM) (Kanada, 2017; Takeichi, 2012)

$1RM \text{ (kg)} = 0.188 + 0.187 \times \text{maximal isometric muscle strength}$. This formula was devised based on examination of 176 in-patient elderlys in Japan (352 legs).

Determination of Hand grip strength (HGS) (Jeong, 2017; Yu, 2017)

- In sitting position with elbow in 90-degree flexion
- Hold dynamometer by the testing hand with the grip meter indicator facing outward, and away from any part of the body.
- Allow 1 practice trial for dominant hand.
- Squeeze the grip with full force and continuously for at least 2 seconds.
- Two trials for handgrip strength test for the dominant hand
- Not to swing the grip dynamometer during the test and not to hold their breaths.
- The time between each trial: ~30s;
- The time interval between trials of the same hand: ~1min
- Verbal encouragement by Physiotherapists.
- HGS will be the average of the reading displayed on the dynamometer in the 2 trials

Determination of limb occlusion pressure (LOP)

- Limb Occlusion Pressure (LOP) is the minimum pressure required, at a specific time in a specific tourniquet cuff applied to a specific patient's limb at a specific location, to stop the flow of arterial blood into the limb distal to the cuff. (Noordin, 2009)

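### The primary outcome is pad force in newtons, which varies with pad position; reproducing the pad distance and analysing torque would reduce avoidable noise in the change score

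*Combined protocol and SAP*

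**What the plan says.** The Primary outcome section states that MVIC of "knee extension of the dominant leg, with a unit Newton (N), will be assessed by computer dynamometry". The bullet above it defines strength more widely, as the "subject's capability for the exertion of force or torque to an external dynamometer over a specified period of time", so both force and torque fall within the plan's own definition.

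The section on determination of MVIC seats the patient with the hip at 90°, "knee flexion of 90°, and the padded force transducer set around malleolus". It says that the lever arm, explained there as the distance from transducer to point of rotation, "will be recorded for calculation of force produced by the computer dynamometer". Three trials are made, and "The highest value for MVIC will be captured for future analysis".

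The test is done at baseline and again once training is complete (Data collection timepoint). The Blinding section assigns the assessments at recruitment and on discharge to physiotherapists who do not know the treatment group.

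Four things are not stated:
- whether the newton value is sensed at the pad or derived from a torque;
- whether the lever arm is recorded at both tests;
- whether the pad must return to its baseline distance at the second test;
- any analysis of torque.

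**The concern.** The knee extensors produce a torque about the knee. The force at the pad is that torque divided by the distance from the knee to the pad. If the pad is strapped a little higher or lower at the second test, the newton value changes although strength has not. This is true whether the device senses force directly or senses torque and divides by a length.

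The malleolus is a landmark region and not a set distance, and the pad is placed afresh about two weeks later. Any difference in distance goes straight into the change in the primary outcome. The plan is sized at 18 evaluable patients per group for 80% power, so it has little room for extra variance. The quantity needed to deal with much of this is already named in the procedure.

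**Working it through.** **1. The plan's own figure.** The Sample size calculation section gives f² = 0.22, power 80%, level 0.05 and 18 per group. Taking the test as two-sided (not stated) and f² as a comparison of two equal groups, d = 2 × √0.22 = 0.938. Then n = 2 × (1.960 + 0.842)² / 0.938² = 17.8, so 18 per group, which reproduces the plan. Power at 18 per group by the same normal approximation is Φ(0.938 × √(18/2) − 1.960) = 80.4%. The exact F calculation gives 78.1%.

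**2. Effect of a pad shift on one reading.** Force = torque / L. At constant torque, moving the pad by s towards the knee changes force by L/(L − s) − 1; moving it away changes force by L/(L + s) − 1. The documents give no L, so 30-40 cm is assumed. The shifts are assumed as well.

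| L | 0.5 cm | 1 cm | 2 cm |
|---|---|---|---|
| 30 cm | +1.7% / −1.6% | +3.4% / −3.2% | +7.1% / −6.25% |
| 35 cm | +1.4% / −1.4% | +2.9% / −2.8% | +6.1% / −5.4% |
| 40 cm | +1.3% / −1.2% | +2.6% / −2.4% | +5.3% / −4.8% |

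**3. Effect on the change score.** With one outcome at two times, the group-by-time test is a comparison of mean changes. Further assumptions, none from the documents: L = 35 cm, MVIC coefficient of variation c = 25-35%, test-retest correlation r = 0.8-0.9, and independent placement error with SD p at each test. The true effect is held at 0.938 SDs of the change score without placement error. In units of the squared mean MVIC:
- variance of change without placement error: 2c²(1 − r);
- variance added by placement: 2(p/L)²(1 + c²).

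Example with c = 0.25, r = 0.9, p = 1 cm: 2 × 0.0625 × 0.1 = 0.0125, and 2 × (1/35)² × 1.0625 = 0.00173. The variance ratio is 1.139 and the SD ratio 1.067. Power is Φ(0.938/1.067 × 3 − 1.960) = 75.1%.

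| Placement SD per test | Rise in change-score SD | Power at 18 per group |
|---|---|---|
| 0 | 0 | 80.4% |
| 0.5 cm | 0.5-1.7% | 79.0-80.0% |
| 1 cm | 1.9-6.7% | 75.1-78.9% |
| 2 cm | 7.2-24.7% | 61.7-74.7% |

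**4. What torque recovers.**
- If the device senses torque and divides by an entered length, multiplying by that same length returns the measured torque exactly.
- If the pad senses force, force × lever arm replaces placement error with error in measuring the length. With a length-measurement SD of 0.5 cm, power is 79.0-80.0%. With 1 cm it is 75.1-78.9%, the same as newtons with a 1 cm placement SD. The gain therefore depends on measuring the length more precisely than the pad is placed.
- If the lever arm is recorded only once, both readings are multiplied by one constant. The patient's percentage change, placement error included, is then unaltered.

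**The case against.** The strongest reply is that the procedure is already partly standardised: joint angles are fixed, the pad goes to a bony landmark and the lever arm is written down. If placement is good to 0.5-1 cm, the loss is about 0.4 to 5.3 power points; larger losses need an SD near 2 cm at each test, for which the documents give no evidence. Newtons also comply with the plan's definition of strength, and returning the pad to its baseline distance would deal with much of the problem without touching the endpoint. All of this is fair, and it keeps the point a modest one. It does not make newtons independent of pad position. Returning the pad will not always be exact, and torque allows for what difference remains.

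Three stronger readings are tempting and are not supported.
- **Bias between the groups.** The assessors are blinded at both tests, so placement error should be unrelated to treatment.
- **Torque removes the error at no cost.** Under direct force sensing, length-measurement error remains, and the documents do not say that the length is recorded twice.
- **Newtons add between-patient spread through leg length, and so distort stratification.** Var(log F) = Var(log T) + Var(log L) − 2Cov(log T, log L), where F is force and T torque. Spread therefore rises only if the covariance is below half of Var(log L). With assumed coefficients of variation of 30% for torque and 6% for lever arm, the break-even correlation is (0.06²/2) / (0.30 × 0.06) = 0.1. Any higher correlation makes force the less variable of the two. The documents do not settle this, so no such claim is made.

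**Conclusion.** The point holds as a precision issue in the primary outcome. The newton value depends on pad distance, the plan does not require that distance to be reproduced, and no torque analysis is planned. The percentages per centimetre are plain arithmetic once a 30-40 cm lever arm is assumed.

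The power figures are illustrations. They rest on assumed variability, retest correlation and placement error, and on the effect size being free of placement noise. If the cited study behind the effect size already contained such noise, part of the loss is already counted, and the figures show what could be gained instead.

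This is a worthwhile, inexpensive improvement. It does not invalidate the trial.

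**What to change.** 1. State whether the newton value is sensed directly or derived from torque.
2. Record the lever arm at both assessments.
3. For the second test, set the pad at the patient's recorded baseline distance.
4. Define the primary outcome as knee-extension torque (N·m) = highest MVIC force × the lever arm recorded at that assessment, and report newtons as a supporting result. Make this change before any results by group are seen. For patients already tested, this correction is possible only where both lengths were recorded.
5. Name separately the scale of the MVIC stratification cutoff, which is to come from recent service data, and the scale of the isometric input to the 1-RM equation, for which no unit is given. The change of endpoint unit must not silently alter either. This point takes no view on which scale the 1-RM equation should use.

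The cost is one repeat length measurement per patient, one multiplication per test, a change of unit in the protocol and the clarifying sentences in steps 1 and 5. No extra strength test is needed.
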